We will use a suite of BrainHQ exercises specifically designed to target and ameliorate disruptions in the 4 general domains described in Figure 1. We will employ basic exercises that focus on increasing processing efficiency in the auditory and visual perceptual and working memory domains, as well as exercises that target impulsivity and cognitive biases. Exercises will be packaged into 4 modules (attention skills, memory skills, executive functioning skills, cognitive control skills) comprised of 4 exercises each. All participants will progress through the same fixed schedule of modules. In each module of training, participants must improve the speed and accuracy of their responses in the targeted cognitive domain of interest. Participants are rewarded on correct trials with points and animations for their performance. Exercises continuously adjust difficulty level to user performance to maintain an approximately 80% correct performance rate. This "Bayesian adaptive" approach, in which the stimulus level at each trial is determined by the participant's responses from all previous trials, determines the level of maximum training efficacy. Compliance and performance will be monitored by data upload following each training session.

Computer Games Control Condition: Participants will play a rotating set of commercial computer games (see Appendix) at the same dose and frequency as the cognitive training. We selected this control activity because it mirrors the game-like properties of the cognitive training and it will be used to control for contact with research personnel and for the non-specific effects of participant motivation and engagement with daily computerized activities. It also allows for a double blind study design. Games from the website Sporcle.com will be used and an online account can be created for each participant. This feature allows the research team to track compliance and progress on the assigned computer games. This approach has been successfully used as a rigorous control condition for computerized cognitive training studies in schizophrenia (e.g., Fisher et al., 2009, 2010; Keefe et al., 2011) and is currently being employed in [name] (consultant) cognitive training study of Veterans with PTSD. The Sporcle.com computer games require low cognitive demand, and based on previous studies, are not anticipated to affect cognitive performance in the proposed training domains.

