Psychosocial Functioning: The 80-item Inventory of Psychosocial Functioning (IPF; Marx et al., 2009), was developed among Veterans to assess level of functional impairment. The IPF includes self-report and behavioral indices that assess current psychosocial functioning across 7 domains. Domain scores are summed to yield a total score for psychosocial functioning.

PTSD Symptoms. The PTSD Checklist – Military Version (PCL-M; Weathers et al., 1993) is comprised of 17 items that correspond to the 17 DSM-IV (APA, 2000) symptoms of PTSD. The PCL-M provides an index of global PTSD symptom severity and will be administered throughout the study. The 20-item PCL-M for DSM-5 is being piloted (Weathers et al., 2012; National Center for PTSD) and will be incorporated upon its release.

Measures: Potential Covariates and Secondary Measures. Potential covariates will be included in an initial analytic model for Stage 2 if deemed necessary (e.g., not evenly stratified through randomization).

Non-Alcohol SUD Diagnoses and Use. Non-alcohol SUD and other Axis-I psychiatric disorders will be determined at baseline with the SCID-I (First et al., 1995), modified for DSM-5. TLFB interview procedures (see above; Sobell & Sobell, 1992) will be used to assess patterns of non-alcohol substance use.

Attention Deficit Hyperactivity Disorder. Conner's Adult ADHD Diagnostic Interview for DSM-IV (CAADID; Epstein et al., 2001) will be administered at baseline to specifically asses for ADHD.

Alcohol Dependence Severity. The 10-item Alcohol Use Disorder Identification Test (AUDIT; Saunders et al.,1993) will be administered at each visit to assess alcohol dependence and harmful and hazardous drinking. Prescription Medication Use: All prescription medications will be documented at baseline. Changes in prescription medication use and dose will be tracked using self-report and the VA electronic medical record.

Training adherence and performance. Number of hours completed and aggregated performance indices (i.e., training effort and dose) will be recorded directly from the computer programs each training week.

AUD and PTSD Treatment: Information on past and concurrent AUD and PTSD treatment will be gathered at each study visit using the Psychosocial Treatment Interview (PTI) (Steketee et al., 1997).

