Stage 2, Aim 2a Exploratory Hypothesis. Changes in global cognition will be significantly associated with decreases in alcohol consumption, PTSD symptom severity and increases in quality of life outcomes. Change scores will be computed for the Global Cognition Score, average drinks per drinking day, the PCL-M and the DUQLS and IPF, by computing the difference between follow-up and baseline. Four Pearson correlations will be performed to test associations between composite index change scores for Global Cognition and the 4 recovery outcomes. Exploratory Mediation and Moderation. We will explore potential mediators (i.e., training adherence and performance) and moderators (i.e., AUD and PTSD severity; Alcohol Use) of the effects of training condition on cognitive outcomes. The MacArthur approach to moderation and mediation analysis (Kraemer et al., 2008) will be employed. These analyses are considered exploratory

because, although the study is powered to detect main effects, we will have power to detect only very strong interaction and mediating effects.

2a.3.k. Timeline for Primary and Secondary Research Activities (See Table 3).

Primary Research Activities. During the start-up phase (months 1-3) of the proposed work, we will coordinate recruitment procedures with the outpatient SUD treatment program, finalize and purchase assessment and training tools and train study personal in the study protocol. A recruitment goal of 4 eligible participants per month was chosen based on prior experiences of the mentorship team who agreed that the goal was realistic and sufficient to meet study objectives, and to allow adequate time to conduct follow-up assessments. Recruitment for Stage 1 will start month 4 and last for 5 months. The weekly and post-training assessments for Stage 1 will be completed in month 9 and 3 month follow-ups will be completed in month 12. We will reserve time during months 13 and 14 to incorporate feedback from Stage 1 to refine the protocol and optimize feasibility for Stage 2. Stage 2 recruitment will begin at month 15 and will last until approximately month 46-47. Therefore, including start-up and Stage 1, all data should be collected by the *middle of year 5*.

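### Training performance is planned as a between-arm mediator, but it comes from two different programs with no common scale, so its mediation result cannot be interpreted as planned

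*Combined protocol and SAP*

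**What the plan says.** The last part of section 2a.3.j (Exploratory Mediation and Moderation) lists the mediators: "We will explore potential mediators (i.e., training adherence and performance". What they are to mediate is the set "of the effects of training condition on cognitive outcomes", so the model compares the two arms. The method named is "The MacArthur approach to moderation and mediation analysis". The plan calls these analyses exploratory and concedes that "we will have power to detect only very strong interaction and mediating effects".

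The only description of the performance variable is in the adherence paragraph of section 2a.3.i, which reads: "Number of hours completed and aggregated performance indices (i.e., training effort and dose) will be recorded directly from the computer programs each training week".

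Section 2a.3.h describes the two programs. In the training arm, "Exercises continuously adjust difficulty level to user performance to maintain an approximately 80% correct performance rate". The control arm plays rotated commercial games on a public site. The plan describes these as undemanding and follows them through the site's own progress tracking.

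The plan gives no formula or unit for performance and no link between the two programs' scores. It does not restrict the performance analysis to the training arm.

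**The concern.** A mediator of a randomised comparison has to be the same quantity in both arms, because the first step of the argument is that condition changes it. Here each arm has its own program and each program has its own scoring. A difference in mean score between arms could reflect what participants did or how the two programs award scores, and the data cannot separate the two.

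At stake is a statement in the trial report that performance does, or does not, carry the training effect on cognition. That statement would have no clear meaning in either direction. The low power that the plan admits is a different matter: it concerns precision, and a larger sample would not cure this problem.

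**Working it through.** **Inputs.** Stage 2 expects 90 completers (section 2a.3.j, Power Analysis) under 1:1 allocation (section 2a.3.g), so 90 / 2 = 45 per arm. The plan gives no figure for the mediation analysis. Its primary power figure reproduces: 128 × 0.70 = 89.6, about 90, and 45 per arm with d = 0.60 and two-sided alpha 0.05 gives 80.4% by the noncentral t (81.2% by the normal approximation), against 80% stated. That figure is used here only to fix the arm size.

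**Structure.** Write the recorded score as c_T + (person's part) in the training arm and c_C + (person's part) in the control arm, where c is set by the program's scoring. The condition-to-performance path is (c_T − c_C) + (true difference). Each program appears in one arm only, so the two terms cannot be told apart.

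- Raw scores: the path contains the unknown offset c_T − c_C.
- Scores standardised within arm: both arm means become 0, the path is 0 by construction, and mediation can never be shown.
- A unit shared by both arms, such as hours or sessions: the path is interpretable, but the measure is then adherence, which is already the other planned mediator.

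**Illustration.** 45 per arm, 3,000 runs per setting, with no causal effect of score on outcome. The following are assumptions, not document figures: condition effect 0.6 SD, ability–outcome correlation 0.5, ability–score correlation 0.6 where present. The plan does not spell out the decision rule. The rule assumed was that the score differs by arm at p < 0.05, and that the score main effect or the condition-by-score term is p < 0.05 in the outcome model.

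| Offset, training minus control (SD) | Both scores track ability: mediation declared | Mean indirect effect, same setting | Only the control score tracks ability: declared | Neither tracks ability: declared |
|---|---|---|---|---|
| −2 | 81.9% | −0.60 | 48.5% | 9.0% |
| −1 | 82.2% | −0.30 | 49.8% | 10.4% |
| −0.5 | 54.4% | −0.15 | not run | not run |
| 0 | 3.5% | 0.00 | 2.5% | 0.5% |
| 0.5 | 53.4% | 0.15 | not run | not run |
| 1 | 81.2% | 0.30 | 48.8% | 9.8% |
| 2 | 83.2% | 0.61 | 48.8% | 9.1% |

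With scores standardised within arm, mediation was declared in 0% of runs.

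Hand check: the within-arm slope of outcome on score is 0.6 × 0.5 = 0.30, so the indirect effect is 0.30 × offset, giving 0.15, 0.30 and 0.60. Its sign and size simply follow the offset. In the last column the arm difference is almost certain and either of two null tests may be significant, so the expected rate is 1 − 0.95² = 9.75%.

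**Hours as the remaining mediator.** Both arms are assigned 30 hours, and section 2a.3.j anticipates comparable adherence. Hours in Pilot #1 (section 2a.2) were 32.79 and 31.38, with only 2 and 3 participants. An indirect effect is (condition-to-hours path) × (hours-to-outcome path). If the first is 0, the product is 0.

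**What a within-arm analysis can detect.** With 45 participants, one covariate, 80% power and two-sided alpha 0.05, Fisher's z gives (1.960 + 0.842) / √(45 − 1 − 3) = 2.802 / 6.403 = 0.438, and tanh(0.438) = 0.41. Only a partial correlation of about 0.41 or more is detectable, before any alpha adjustment.

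**The case against.** The strongest reply is that the index is undefined and has been read unfavourably. The gloss of effort and dose in section 2a.3.i leaves room for a common-unit measure, and use is tracked in both arms. A reader might infer that the mediation result is bound to be a scale artefact. The documents do not support that certainty, because it depends on which index is chosen. Even so, the reply does not rescue the analysis. Sections 2a.3.g, 2a.3.i and 2a.3.j each list performance separately from adherence, engagement or hours, and a common-unit index would largely repeat the adherence mediator.

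A reader might also infer that performance is nearly constant in the training arm because of the 80% target. That would follow only if performance meant percent correct, which the plan nowhere says. Difficulty adapts, and "the stimulus level at each trial is determined by the participant's responses from all previous trials", so the level reached can differ between people. The level has no documented counterpart in the games, so the lack of a common scale remains.

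The high simulated rates rest on assumed offsets and assumed links between score and ability, as the table shows. That is a fair limit on the size claimed.

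Finally, the analysis is labelled exploratory, its low power is admitted and alpha is adjusted for exploratory tests. This limits the consequence. It does not give an uninterpretable path a meaning.

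**Conclusion.** The concern holds in a limited form. As planned, a between-arm mediation result for performance cannot be interpreted, because no index or scale common to both programs is defined and within-arm standardising removes the very path under test. If percent correct were the index, the adaptive target would also remove most of its spread in the training arm.

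The documents fix no magnitude. Under the assumptions above, false declarations of mediation range from 3.5% with no offset to 83.2% with a large one when both scores track ability, and stay near 10% at offsets of 1 to 2 SD when neither does.

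The importance is minor. The primary test on the Global Cognition Score, the secondary tests and the sample size are untouched.

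**What to change.** Amend the mediation text in section 2a.3.j as follows.

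- Remove performance as a mediator of the condition effect. Keep only measures recorded in the same unit in both arms, such as hours completed, and state that if adherence is balanced as expected, hours cannot mediate the effect either.
- Analyse BrainHQ performance in the training arm only: regress follow-up Global Cognition Score on a prespecified index that is free to vary, adjusting for baseline score. Gain in difficulty level is a candidate, provided the program's recorded indices include it. The plan does not say that they do, nor how levels would be combined across the 16 exercises (4 modules of 4), so both must be settled first.
- Report this as a predictor analysis. Label it non-randomised, open to confounding by ability and motivation that baseline adjustment may not remove, and based on about 45 completers.

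The cost is a sentence or two of text and a check of what the software records. The pooled performance mediation test is given up, and the within-arm analysis that replaces it uses half the sample and answers a narrower question.
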